How does screening intervals of between 15 and 27 months, compared with intervals of between 28 and 40 months affect cancer stage at diagnosis, treatment associated morbidity, and false positive recalls in women attending breast cancer screening age 50-70 years? (analysis led by [name], carried out at Bristol)

We will use the 'clone, censor and weight' approach described by Hernán.(25) Women will be eligible if screened between ages 50-70 years, and follow-up will start 15 months after the date of first invitation to screening. Follow-up for each woman will be duplicated ('cloned'), with one copy assigned to each treatment strategy. Follow-up for each cloned copy will be until women deviate from the strategy assigned that copy, because they are invited to screening too late (in the more frequent screening group) or too early (in the less frequent screening group). We will model the probability of being screened over time, in order to derive inverse-probability of screening weights. Moving house (and screening centre) will be included as a covariate, as this can prompt a shorter screening interval. These weights will be used to adjust for the selection bias introduced by censoring follow-up at the time of deviation from assigned treatment strategy. Planned shorter screening intervals due to suspicious findings at baseline will be excluded.

Additional analyses of will be conducted to investigate whether the effects of screening interval on health outcomes vary according to age group at screening (50-60 or 61-70 years).

Different definitions of round length will be investigated if time permits. This may include women attending family history screening and/or women whose round length was delayed by the COVID-19 pandemic.

How does recall threshold affect all-cause and breast cancer specific mortality, overdiagnosis, treatment associated morbidity, and false positive recalls in women attending breast cancer screening age 50-70 years? (analysis led by [name] and [name], undertaken at Birmingham and Warwick [[name] and [name] working across both universities])

We will estimate the effect of screening threshold, using instrumental variable approaches or other analyses with consideration of causal inference. The exposure or instrumental variable will be the rate of recall of the previous 5000 cases screened by the reader (or reader pair). The readers' recall rate for previous cases may be an appropriate instrumental variable to because its effect on the outcome (for the current case) is only via the readers' threshold for the current case. This assumption will be evaluated. Instrumental variable definitions will be finalised in preliminary analyses that aim to maximise their association with recall probability, in datasets from which all outcomes have been removed. At this stage we will consider different numbers of previous cases to inform the instrumental variable definition. 5000 represents the mandated minimum per year for each reader, according to English quality assurance guidelines(26) and would give a reasonably precise estimate of recall threshold (if

the reader recalled 4% of cases the 95% binomial exact CI is 3.5% to 4.6%). We know there is substantial inter-reader variability in recall threshold, and intra-reader temporal changes (changes within a single reader over time) are much smaller, justifying increasing the number of previous cases to reduce statistical variability in the instrumental variable. We will conduct sensitivity analyses to assess whether results are robust to changes in the instrumental variable definition. We have data for a full range of thresholds for every year since 1988, and therefore have sufficient data to adjust for temporal changes. We will model changes in rates of outcome with calendar time using cubic splines.

Three models will be developed for three time horizons (shown in brackets): 1: The effect of threshold at the final screening round (27 years) with adjustment for previous attendance record, so follow-up is not contaminated with screening invitations. 2: The effect of threshold in a screening round (3 years), adjusting for clustering of screening episodes within women, the women's age at screening, and previous attendance patterns, with outcomes limited to false positive recalls, interval cancers, and stage of cancer detection. 3: If feasible, the cumulative effect of threshold over all screening rounds including the woman's entire screening history and follow-up post screening (27 years)

Modern mammography screening in England uses two readers and arbitration of discordant assessments. Any subsequent intervention to change the recall threshold would most likely act upon each individual reader. We will use modelling approaches to evaluate the impact of test threshold on screening outcomes; we will investigate the impact of changing the process (adjusting the threshold of both readers), changing the threshold for an individual reader, the impact of one vs two readers, changing the threshold for one or both, and the pairing of readers. We will use instrumental variables to describe the recall threshold of each reader, in these proposed models. We will also model the overall effect of changing recall threshold, using a predictor for the single readers decision in the older cases where there was only one reader, and the reader combination's combined threshold in later years. This will show the relationship between the recall threshold of the system and women's outcomes.

We will investigate the mechanism of action of any effects, through intermediate outcomes. For example we expect that reduced recall threshold may increase cancer detection but change the spectrum of disease identified towards more small cancer detection (possibly of low histological grade) and also DCIS, which may in turn affect mortality and overdiagnosis. This will help our understanding of what we should aim to detect at breast screening.

A further exploratory analysis of instrumental variable approaches to recall threshold specifically for DCIS will be undertaken, as DCIS is detected predominantly through microcalcifications, and there is vigorous debate about the benefits and harms of detecting DCIS.

We will also investigate the variability between centres and readers, and its implications for screening QA targets.

Additional analyses will be conducted to investigate whether the effects of recall threshold on health outcomes vary according to age group at screening (50-60 or 61-70 years).

Sample Size Requirements

This observational data analysis does not require a formal sample size calculation. We will include every eligible case within the available cohort in analyses. However, we have included some calculations here to ensure that there are sufficient available data to enable meaningful analysis. Previous analyses have shown clustering of the proposed outcomes within centres and readers is negligible ($ICC << 0.0001$), hence the cluster of observations is

not accounted for in these calculation; however, we will adjust for these in the analyses where appropriate.

Table 1. Sample size requirements for detecting differences within the dataset. All calculations are for 90% power at 5% significance level. There are more than 30 million screening appointments in the dataset, from more than 10 million women.

Outcome	Baseline value	Change in value	Number required in each group to detect
Intermediate outcomes			
Recall rate	3.9%	0.1%	777,920
Cancer detection rate at screening	8.4/1000	0.5/1000	679,499
Small invasive cancer detection rate at screening	3.4/1000	0.3/1000	756,401
Interval cancer over 3 years	2.9/1000	0.3/1000	640,353
False positive recalls	3.1%	0.1%	641,114
Health outcomes			
All-cause mortality	0.6050 per 100 person-years	0.6025 per 100 person years	804,400
Breast Cancer mortality	0.0443 per 100 person years	0.0433 per 100 person years	880,116
Overdiagnosis	1.3% of women invited for screening for 20 years(1)	0.1%	279,869

We will deliver three journal articles, one for each of the three questions investigated: age of eligibility; recall threshold and round length. We will submit a fourth journal article exploring the link between detection of different cancer types and outcomes, with a focus on DCIS in particular. We will also present results to the UK National Screening Committee, and inform redrafting of the English national quality assurance standards for breast screening (see work package 3).

Work Package 3: Pathway to impact (Led by [name], PHE and [name], Warwick)

In addition to journal publication there are three strands to our dissemination strategy. 1. Influencing national policy directly via the UK National Screening Committee 2. Influencing national practice through national professional guidance and communication to health professionals 3. Communication to the public

1. Influencing national policy directly via the UK National Screening Committee (UKNSC)

The UK National Screening Committee is responsible for all national screening policy, including making major changes to screening programmes such as age of eligibility or frequency of screening. We will present our results in person to the UK National Screening Committee Adult Reference Group (ARG) which is responsible for all adult screening programmes (on which [name] sits). If our results suggest that a major change is appropriate then we will submit a formal request via the annual call or directly to the ARG, and the UKNSC would then undertake a systematic review putting our research into context and make a national decision on that basis. These decisions are directly

nationally implemented with associated budget so encounter fewer barriers to implementation than guidelines.

We will provide evidence on how the changes would affect the benefits and harms of screening overall, and on how the changes would differentially affect women of different socioeconomic status (using our analysis of a proxy for this, Index of Multiple Deprivation). This will allow the UK NSC to consider the implications of any decision on inequalities, as required by UKNSC criterion 12. (There should be evidence that the complete screening programme (test, diagnostic procedures, treatment/ intervention) is clinically, socially and ethically acceptable to health professionals and the public).

The UK National Screening Committee will be involved throughout the process, with [name] (UKNSC chair) and [name] (Director of PHE Screening) joining our national policy advisory group, [name] (Chair of ARG) a co-applicant, and regular written updates given to key personnel such as [name] (PHE Screening evidence lead). Letters of support from [name] and [name] are attached (appendix 1)

2. Influencing national practice through national professional guidance and communication to health professionals

If our research were to suggest that there is a need to reduce variability in screening intervals, or change test threshold this would be implemented through national professional guidance, changes to the breast screening programme specific operating model,(27) and influencing changes to practice. Here [name] (Professor of Implementation Science, co-applicant) is advising on strategies to maximise implementation. Our approach will be:

- i. To engage in the process of redrafting the national professional guidance,
- ii. To identify and engage national champions for practice change who will drive change through their networks.

Redrafting the national professional guidance: Our findings will be used to inform the regular update of the NHS Breast Screening Programme Consolidated standards, and the Professional Guidance for Breast Cancer Screening Radiology (objective 3, led by [name], Breast Screening Research & Data Lead, PHE Screening). These are used by commissioners to develop the service specifications when commissioning breast cancer screening, by the screening QA service to inform quality interventions and by radiologists in assessing their own performance. We will use the findings from objectives 1 to 3 to propose changes to quality metrics to align with maximising benefit and minimising harm, cognisant of effects on inequalities (via the Index of multiple deprivation proxy), and of statistical variability and the need to define targets measurable every year at each centre. Our analysis of threshold will inform consideration of targets for recall rate (currently <5%), invasive cancer detection rate (currently $\geq 5.7/1000$), small cancer detection rate (currently $\geq 3.1/1000$), DCIS detection rate (currently $\geq 0.6/1000$, all for previous attenders), and round length (currently 3 years). (26, 28) PHE are implementing a live data monitoring system, so centre-level performance towards QA targets can be measured. PHE will consult widely in developing revised guidance and standards, engaging a wider range of practitioners to identify practical issues, misunderstandings, attitudes, and context from a wider range of stakeholders including radiologists who are less research-involved, and radiographers, pathologists, breast clinicians, breast care nurses, administrative staff and centre managers. Whilst the guideline development is led by Public Health England, implementation through commissioning is the responsibility of NHS England. [name], Head of Public

Health Commissioning and Operations for NHS England and NHS Improvement, and [name] (regional NHS England) will sit on our advisory group. They will advise early throughout the study on how practice may be influenced through commissioning, including barriers and enablers.

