Main data set (objective 1a): Our research team have already linked breast screening data from 80 English centres with English Cancer Registry and civil registration s mortality file data for 10 million women attending 35 million breast screening appointments, between 1988 and 2018 ([name], POSTBOx, NIHR, 572k). Data were extracted from centres up to 2018, but a date cut-off of date of first offered appointment up to end Dec 2016 was implemented in the previous data transfer to Warwick (for the previous POSTBOx project). The dataset for ATHENA-M will be based on this same database, but with the following additional data transferred to Warwick for analysis i. An additional 3 million women, who were offered screening but never attended, to enable intention to treat analysis ii. an additional outcome of cause of death, in particular breast cancer death. iii. Updated linkage to more recent follow-up in cancer registry to end 2018 and civil death registration to date of linkage in 2021. This transfer will be in two parts. Firstly, the expanded dataset with the extra 3 million women, without updating linkages or adding the extra outcome of cause of death. This first dataset will ensure there are data available in the event of issues arising in the reorganisation of Public Health England. The second transfer will contain updated linkages to the cancer registry (to end 2018/2019 as available) and civil death registration (to 2021), and extra outcomes of cause of death. Further updates to the database based on later extracts from NBSS (post 2016) and updated linkage to civil death registration, cancer registry and/or BSselect may be made to ensure these data are as current as possible. Summary of requested tables is in appendix 2, and full definition of all variables is in a separate document. Inclusion criteria is in appendix 3. This cohort definition gives 2.3 million women invited never screened between 1988 and 2016 when aged 47 to 73. These are additional to the 10.5 million women with at least one screened episode between 1988 and 2016 when aged 47 to 73.

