1. Interval cancers detected within 3 years of screening. An interval cancer is a cancer detected symptomatically in the interval between breast screening appointments. These are all biopsy proven, with records taken from the English Cancer Registry. It is a binary outcome for each episode of screening for each woman. We will use the NBSS data to exclude screen detected cancers from this measure. Interval cancers has been identified by the UK National Screening Committee, Public Health England and our PPI team as an important intermediate outcome because reducing interval cancers is not associated with increasing overdiagnosis in the same manner as number of cancers detected.
2. Cancers detected at screening, taken from the results of screening recorded by the Breast Screening Programme in the National Breast Screening Service (NBSS)

database. It is a binary outcome for each episode of screening for each woman. These are all biopsy proven as per screening programme standards. Definition includes any invasive cancer or Ductal Carcinoma in situ (DCIS) or Lobular Carcinoma in Situ (LCIS) of the breast, using standard definition of cancer registry and screening programme) with subgroup with invasive cancer only also reported. Records are complete because there are quality assurance mechanisms to ensure complete recording of these as part of the standard KC62 reporting procedures.

3. Screen detected cancer characteristics. This is defined by variables from the English Cancer Registry, including histological grade, cancer stage, and cancer size. These intermediate outcomes were chosen because the proposed mechanism of action of breast screening benefit is through detection of smaller earlier stage cancers. This outcome can be difficult to interpret as increased detection may be associated with mortality benefit or overdiagnosis harm. This will be measured for screen detected cancers only, (and for a combination of screen and symptomatic cancers, where differences between exposed and unexposed represents the stage shift of exposure: see stage shift outcome). [In detail TNM stage (size, nodes, distant metastases), alternative nodal count to match Z11 and POSNOC trials 1/1-2/3+, DCIS vs invasive, invasive grade 1/2/3, DCIS grade 1/2/3, DCIS surgical size (mm), Invasive surgical size (mm), invasive cancer type, hormonal status, Nottingham Prognostic Index].

Health Outcomes or close proxies (Primary outcomes)

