Appendix 1 – Letter of Support [redacted]

Appendix 2: Data requested and reason

Table 1: National Breast Screening Research Dataset (NBSRD) Patient Demographics data to be provided to the applicant in accordance with the cohort inclusion and exclusion criteria.

To include one row per woman included, with pseudonymised identifiers to link between tables, with ethnicity, month and year and cause of death, month and year of birth, participation in relevant research trials, and issues with data quality of NHS number.

Table 2: National Breast Screening Research Dataset (NBSRD) breast screening episode data for routine population screening episodes to be provided to the applicant in accordance with the cohort inclusion and exclusion criteria

To include one row per screening episode, with pseudonymised identifiers to link between tables, screening date, pseudonymised identifiers for the radiologists examining the mammograms, their decisions, whether the woman was recalled for further tests, whether cancer was detected.

Table 3: National Breast Screening Research Dataset (NBSRD) mammographic features to be provided to the applicant in accordance with the cohort inclusion and exclusion criteria.

Details of mammographic features associated with detected cancers. Data will be provided for screen detected breast tumours only. Features to include side of the body, mammographic characteristics such as mass or calcifications.

Table 4: National Breast Screening Research Dataset (NBSRD) cancer tumour data to be provided to the applicant in accordance with the cohort inclusion and exclusion criteria.

Tumours will be limited to C50 (breast cancer) or D05 (Breast DCIS or LCIS) records, or the pre-1995 equivalents in of '174' and '2330' respectively, only, inclusive of both screen detected and symptomatically detected breast tumours. Includes ICD classification, morphology, behaviour, grade, size, number of involved nodes, oestrogen, progesterone and HER2 status, Nottingham Prognostic Index, TNM stage, and whether screen detected.

Table 5: National Breast Screening Research Dataset (NBSRD) cancer treatment data to be provided to the applicant in accordance with the cohort inclusion and exclusion criteria.

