Appendix 3 Inclusion criteria

Women need an episode record (ODR Table 2) with date of first offered appointment (DOFOA) and age at DOFOA recorded and at least 1 demographics record (ODR Table 1) in order to be selected for the ATHENA-M cohort. So the ATHENA-M proposed cohort we are currently working towards is as follows (all dates are given for main project extract, there may be an initial extract with earlier dates and a subsequent extract with updated dates):

Women invited to routine population breast cancer screening in England from screening programme inception in 1988 to December 31st 2016, who:

- (i) Were aged 47 – 73 years at their routine screening invitation*
- (ii) Have at least one demographics record, required for linking*

The inclusion criteria by table are as follows (again for the main project extract)

- *Table 1: NHS National Breast Screening Programme (Patient Demographics) NBSS data will be restricted to women meeting the inclusion criteria.*
- *Table 2: NHS National Breast Screening Programme (routine episode) data will be restricted to women in Table 1. Records with no invitation to screening will be excluded from Table 2. Table 2 will be restricted to records with date of first offered appointment either (i) null or (ii) from screening programme inception in 1988 to 31/03/2018.*
- *Table 3: NHS National Breast Screening Programme (assessment procedures - mammographic features) NBSS data will be restricted to women in Table 1 and episodes in Table 2.*
- *Table 4: Cancer Registry data will be restricted to C50x or D05x records, or the pre-1995 equivalents in of '174' and '2330' for all women identified in Table 1, irrespective of whether the tumour was screen detected, where DATEOFDIAGNOSISBEST is between 01/01/1988 and 31/12/2018.*
- *Table 5: Cancer Registry data will be restricted to events linked to the tumours identified in Table 4 and where the event occurs within the first 365 days from DATEOFDIAGNOSISBEST and the OPCS4_CODE is identified in Table 10: Reference table OPCS4_codes. All other event data will be excluded.*

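### As written, some cancers found at screens after 31/03/2018 would be counted as interval cancers, because the registry data run nine months past the NBSS episodes used to exclude them

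*Protocol*

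**What the plan says.** The outcome is item 1 under Intermediate outcomes (Work Package 2, Measuring Outcomes): "Interval cancers detected within 3 years of screening. An interval cancer is a cancer detected symptomatically in the interval between breast screening appointments". It is binary for each screening episode. On source: "These are all biopsy proven, with records taken from the English Cancer Registry". On separating the two modes of detection: "We will use the NBSS data to exclude screen detected cancers from this measure". No other filter is named there.

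Appendix 3 fixes the dates of the main extract:

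- Routine episodes (Table 2) are limited to first offered appointments that are null or "from screening programme inception in 1988 to 31/03/2018". Non-routine episodes (Table 7) have the same end date.
- Registry tumours (Table 4) are included "where DATEOFDIAGNOSISBEST is between 01/01/1988 and 31/12/2018".

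The Main data set paragraph of Work Package 1 allows the second transfer to carry registry data to the end of 2018 or 2019. It adds that later NBSS extracts may be made, without committing to them. Appendix 2 lists, among the Table 4 tumour variables, "TNM stage, and whether screen detected". It does not say where that item comes from, and the outcome definition does not use it.

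**The concern.** The events come from one source and the exclusions from another, and the source of exclusions ends first. For the last nine months of registry data, a cancer found at a routine rescreen looks the same as a symptomatic one, because the episode that would identify it was not extracted.

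For example, a woman is screened in August 2015, rescreened in June 2018 and diagnosed in July 2018. Her cancer enters from the registry at 35 months, and no June 2018 episode exists to exclude it. August 2015 is scored as an interval cancer. With all dates three years earlier, the same history would be scored correctly.

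This is a different problem from incomplete follow-up. Screens in mid to late 2015 have a full 36 months of registry data, and the error adds events to them. Interval cancer is one of only three outcomes in recall-threshold model 2, and the affected screens are the most recent ones with a complete 3-year window.

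**Working it through.** **The plan's own figure.** Table 1 (Sample Size Requirements) gives 640,353 per group for interval cancer, 2.9 against 2.6 per 1000, with 90% power and 5% significance. With p̄ = 0.00275 and two-sided testing,

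n = [1.960·√(2p̄(1−p̄)) + 1.282·√(p₁(1−p₁) + p₂(1−p₂))]² / (p₁−p₂)² = 640,353 (unrounded z values, rounded up).

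The figure reproduces and is not in dispute.

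**Length of the gap.** From 31/03/2018 to 31/12/2018 is 275 days, or 9.0 months. To 31/12/2019 it is 21.0 months.

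**Inputs from the protocol.** About 2 million attenders a year (Background and Rationale); 8.4 screen-detected cancers per 1000 screens and 2.9 interval cancers per 1000 (Table 1); 35 million appointments (Work Package 1).

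**Assumptions, not in the protocol.** Round length L is normal with mean μ = 35 to 37 months and SD σ = 2 to 3. A share a = 70 to 80% of screened women attended the previous round. Diagnosis follows the screen by one month, so a miscounted cancer needs L < 35.

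**Pool of cancers.** Screens produce 2,000,000/12 × 8.4/1000 = 1,400 screen-detected cancers a month. With the one-month lag, screens from April to November 2018 reach the registry by 31/12/2018: 8 × 1,400 = 11,200.

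**Total false events.** Count only index screens up to 31/12/2015, which have 36 months of registry data. A rescreen t months after 31/03/2018 then counts if t + 27 < L < 35, so

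false events = 1,400 × a × ∫₀⁸ [Φ((35−μ)/σ) − Φ((t+27−μ)/σ)] dt.

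| μ | σ | a | integral | false events | share of 101,500 |
|---|---|---|---|---|---|
| 37 | 2 | 0.70 | 1.103 | 1,081 | 1.1% |
| 36 | 2.5 | 0.75 | 2.181 | 2,290 | 2.3% |
| 35 | 2 | 0.80 | 3.202 | 3,586 | 3.5% |

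The denominator is 35,000,000 × 2.9/1000 = 101,500. The first and last rows are the extremes over the assumed ranges.

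**Per index screen.** For a screen k months before 31/03/2018 (27 ≤ k ≤ 35),

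added rate per 1000 = 8.4 × a × [Φ((35−μ)/σ) − Φ((k−μ)/σ)].

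With μ = 36, σ = 2.5 and a = 0.75, the multiplier is 8.4 × 0.75 = 6.3:

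- k = 35 (end of April 2015): 0
- k = 33 (end of June 2015): 6.3 × (0.3446 − 0.1151) = 1.45
- k = 27 (end of December 2015): 6.3 × (0.3446 − 0.0002) = 2.17

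So screens from July to December 2015 gain about 1.5 to 2.2 per 1000. Without the diagnosis lag, the affected period starts at about April 2015.

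**The case against.** The strongest reply is that the definition already requires symptomatic detection. A cancer found at a June 2018 screen fails it, and the NBSS sentence only names a tool. Appendix 2 requests a screen-detected item for every tumour, so the means to avoid the error may be in hand. The Appendix 3 dates are provisional, later NBSS extracts are possible, and data-quality work on misclassification is planned. A follow-up end date is also the sort of detail that a separate analysis plan may settle.

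Part of this stands: miscounting follows from the written rule and dates, and is not certain to happen. But the protocol fixes the rule and both dates, and together they do not deliver the definition. The screen-detected item has no stated source; if it derives from NBSS linkage, it has the same gap. Later extracts are optional.

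Three stronger readings are tempting and are not supported.

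- *Every cancer found at a screen after 31/03/2018 is miscounted.* Only those less than 3 years after an earlier screen can be. In a three-yearly programme many rescreens fall at or beyond 36 months.
- *The error hides or reverses the effect of recall threshold.* The exposure in model 2 is the recall rate of the reader or pair at the index screen. Nothing says the same readers read the 2018 screen, and a low index threshold could leave fewer cancers to find in 2018. The direction is open. Calendar-time splines may also absorb part of a shift common to all units, although they do not correct the outcome.
- *False positive recalls and the sample size are affected too.* False positive recalls come wholly from NBSS and stop with it. Table 1 is unchanged.

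**Conclusion.** The point holds in a limited form. The stated rule and extract dates misclassify some screen-detected cancers as interval cancers, and nothing in the protocol closes the gap. Across the whole dataset the inflation is modest. It is concentrated in index screens from about April 2015 onward, where the mid-range estimate for the second half of 2015 is several times the 0.3 per 1000 that Table 1 sets out to detect. Both sizes rest on the assumed round length, previous attendance and diagnosis lag, and on applying 8.4 per 1000 to all rescreens. They would grow if the registry ran to end 2019 with NBSS unchanged. Interval cancer is an intermediate outcome, so the primary outcomes are not touched. The definition should be corrected before analysis because the correction is cheap.

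**What to change.** In item 1 of Intermediate outcomes, state that ascertainment of interval cancers ends at the last date covered by the NBSS episode extract in use (31/03/2018 in the main extract), and that follow-up after that date is censored. The complete 3-year binary outcome is then available for screens up to 31/03/2015.

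Alternatively, keep the later registry diagnoses and classify those after the NBSS end date with the screen-detected item in the Appendix 2 tumour table (Table 4). First confirm that the item does not derive from NBSS, and check it against NBSS in earlier years.

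The first option costs one sentence, one date in the code and about nine months of interval-cancer follow-up. The second costs a small validation exercise. Neither needs new data. If a later NBSS extract arrives, the end date moves with it.
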